13.1 INTRODUCTION

Each ACCESS Clinical Center must be certified for screening patients and performing physical examinations and spirometry in order to recruit and examine cases and controls for ACCESS. The staff who will be performing ACCESS test procedures, interviewing ACCESS cases and controls, and completing ACCESS data collection forms and performing data entry must attend a training session or be trained by a certified person and demonstrate proficiency in the procedures they will perform during the study in order to be certified.

13.2 CLINICAL CENTER CERTIFICATION

In order for an ACCESS Clinical Center to be certified to screen cases, the Clinical Center must submit to the Clinical Coordinating Center (CCC) documentation of Institutional Review Board (IRB) approval of the ACCESS Protocol and Consent Forms. Copies of the Consent Forms were submitted before recruitment was started and whenever the forms are revised. Notification of IRB approval in each Clinical Center is also required annually. Conflict of Interest Statements (see Chapter 5) for appropriate ACCESS staff members are required for certification and these forms are to be submitted annually. In addition, the ACCESS Clinical Center must have at least one certified research coordinator, one physician certified to perform physical examinations, one individual certified to perform data entry, one individual certified to use the ATRS, and a certified Spirometry Laboratory.

In order to be certified to enroll cases and controls into ACCESS, the Clinical Center must have the facilities and staff to collect, analyze and ship blood specimens and certified staff to interview cases and controls and to operate the distributed data management system at the Clinical Center.

13.2.1 Spirometry Laboratory

The Spirometry Laboratory in the Clinical Center Pulmonary Function Laboratory should adhere to the American Thoracic Society standards (Crapo et al, 1995) for performance and quality control of spirometry. The quality control procedures for performing spirometry in the local Pulmonary Function Laboratory should be documented in a log as follows:

- a) 3L calibration syringe check daily;
- b) Leak check daily;
- c) Linearity check weekly;
- Repeat spirometry performed on healthy lab staff member(s) or other volunteer(s) to check for consistency monthly; and
- e) Spirometry thermistor compared to a reference thermometer monthly.

This log must be available for review during site visits.

Each set of tracings for the ACCESS cases are to be reviewed by the Clinical Center Principal Investigator or designated Co-Investigator to determine that there is less than 5% variability among the three tracings for each patient. The spirometry tracings for the first three patients enrolled in each Clinical Center are requested by Clinical Coordinating Center staff who arrange for quality assurance review of those tracings.

13.3 CERTIFICATION OF INDIVIDUAL ACCESS STAFF MEMBERS AND FACILITIES

13.3.1 Research Coordinator / Interviewer

In order for a person to be certified as a Research Coordinator / Interviewer in ACCESS, the person must attend a training session, or be trained and tested by a certified Research Coordinator / Interviewer. The certification process includes a test on the methods and procedures of ACCESS and knowledge of the ACCESS interviewing procedures. The person completes one successful practice session registering a case or control using the Automated Telephone Response System (ATRS). The person completes and submits to the CCC two copies each of the ACCESS Demographics and Medical History Questionnaire (Form 10), Family History Questionnaire (Form 22), and the Occupational and Recreational Questionnaire (Form 12) using data from sarcoidosis patients known at the Clinical Center. The completed forms are submitted with a completed Request for Certification.

13.3.2 Physical Examination Physician

The Principal Investigator of an ACCESS Clinical Unit notifies the Clinical Coordinating Center that an ACCESS physician is certified to perform physical examinations on ACCESS patients by signifying that the physician understands the ACCESS protocol, including the procedures that he/she is to perform and has taken a test on the methods and procedures associated with the ACCESS protocol.

13.3.3 Data Entry Personnel

The individuals certified to enter data using the distributed data management system may be research coordinators or other designated Clinical Center staff.

It is the responsibility of the Clinical Center Principal Investigator to determine who is responsible for collecting data, and who is responsible for entering data into the ACCESS database. The person responsible for entering data must attend a training session or be trained by a certified data entry person. Once trained, the candidate must enter data for two forms each of the: Demographics and Medical History Questionnaire (Form 10), the Family History Questionnaire (Form 22), and the Occupational and Recreational Questionnaire (Form 12) using completed forms from the CCC that are sent to the Data Entry Applicant. These data and applicant information are electronically transferred to the CCC during regularly scheduled data transmission. The records generated from the practice forms are compared to the study standard forms at the CCC, and the applicant is notified of any discrepancies. Once the material has been received in a satisfactory format, the Clinical Center Principal Investigator is notified that the Data Entry Applicant has been certified and a permanent certification number is assigned.

13.3.4 ATRS Staff

C-TASC staff have established a system to allow authorized personnel to practice a few registrations without actually entering a case. The same procedures are used for this practice session as for an actual registration except that: when requested to enter the Clinic Password, enter 9999 rather than the Clinic Password that has been assigned to the Clinical Center. The ATRS identifies this call as a practice session. Follow the instructions as if a case were actually being registered or enrolled. Use 999-9999 as the practice ID number. Each individual authorized to register or enroll patients should practice at least once to be certified to use the system for cases and controls. The practice session should be performed during working hours, weekdays 9:00 a.m. - 4:00 p.m. so that problems can be resolved if they occur. At the end of the practice session, the system indicates the status of the practice session. The practice system will remain in place for the duration of the study. If Clinical Center staff think they need some practice using the system after certification, or if new personnel are assigned to register cases and controls, the practice system can be used for this purpose.

13.4 RESPONSIBILITIES OF THE CLINICAL COORDINATING CENTER IN TRAINING AND CERTIFICATION

The responsibilities of the Clinical Coordinating Center in training and certification are as follows:

- 1. Assist in organization and presentation of training sessions.
- 2. Review of forms submitted by ACCESS personnel as part of certification requirements and communication of concerns to those personnel.
- Coordinate results of review of certification materials submitted by personnel at Clinical Centers.
- Maintain documentation of the various aspects of certification requirements which have been completed or need to be completed by Clinical Centers and individual staff.
- 5. Issue certification numbers to certified individuals.

CHAPTER 14

QUALITY ASSESSMENT PROCEDURES

14.1 INTRODUCTION

A primary concern for every study is to assure the quality of data being collected and analyzed. The validity of the reports and results produced and published by the study depends upon the integrity of the data submitted by the Clinical Centers and core facilities and upon the appropriateness, thoroughness, and correctness of the data processing and data analysis procedures carried out by the Clinical Coordinating Center (CCC) staff. The first step in assuring quality data is to have the data collectors and observers properly trained, certified and periodically recertified. Standard procedures for pulmonary function testing and bronchoalveolar lavage (BAL) specimen processing are used in this study. This is supplemented with various procedures to monitor the performance of staff with respect to the quality of the study data they have reported. The CCC staff implemented a quality assurance plan developed in collaboration with the Steering Committee and NHLBI. Procedures for monitoring the performance and quality of submitted data and specimens from the Clinical Centers, the core facilities, and the Clinical Coordinating Center are given in the following sections.

14.2 QUALITY ASSESSMENT OF THE CLINICAL CENTERS

14.2.1 Performance Reports

Performance of the Clinical Centers with respect to case and control recruitment is assessed in weekly reports. These reports include the number of cases and controls enrolled to date and ratio of the number enrolled to the number who should have been enrolled to date given the scheduled recruitment period already completed. Each matched control should be recruited into the study shortly after the corresponding case. In addition, the CCC staff provide information about the number of women and minority cases being recruited into the study in monthly reports. Performance in other areas is assessed by consideration of the following at quarterly intervals.

- For enrolled cases and matched controls, the number of study forms which are past due at the Clinical Coordinating Center, based on each case's date of enrollment.
- 2. Specimens which are past due at the core facilities.
- Studies (e.g., pulmonary function tests or chest X-rays) which are called for by Protocol but were not performed.
- 4. Time between enrollment of case and enrollment of matched control.
- 5. Number of Protocol violations.
- 6. Number of forms that passed the first edit and number of forms passing the current edit.
- 7. Percentage of cases enrolled in Clinical Course Study with missed telephone contacts and percentage of cases who are inactive, i.e., are no longer willing or able to have the two-year examination.

The CCC staff compares performance and quality of submitted material among Clinical Centers; the areas considered include number of forms past due, studies not performed, or specimens improperly prepared or improperly labeled, etc. The CCC staff also compare each Clinical Center's quarterly performance to its own past performance and to agreed upon study standards, in order to determine whether the Clinical Center's performance is outside study standards or whether the level of performance has worsened substantially compared to its previous record. Study standards are set by weighing how crucial an item is to the study Protocol and the levels of performance which past experience has shown to be attainable.

In addition to the above analyses, performance reports include summary statistics for each Clinical Center. Large changes in these statistics from period-to-period within a Clinical Center may indicate changes in the way data are being collected. Comparison of these statistics across Clinical Centers could suggest either differences in how data are collected or differences in the patient population, and may prompt further investigation.

14.2.2 Re-Abstraction of Selected Data for ACCESS Cases and Control

For selected cases and controls participating in the etiology study, CCC staff identify tape recordings that will be used for re-abstraction of the case's or control's interview data and the form to assess quality of data entry. The tape and copies of study forms for each case or control are sent to the CCC for review and comparison with the study forms and the data entered in the computer database. Clinical Coordinating Center staff listen to the tape to ascertain whether the interviewer adhered to study procedures in conducting the interview and complete a form to record this assessment. Specifically the reviewer determines whether the interviewer followed the ACCESS script for the interview, and provided good anchors for the time frames (e.g., listing significant events occurring during the reference period) being used in the interview and for the tape the reviewers confirm the responses of the case or control were recorded correctly for a sample of items on the forms and that the responses match the data entered in the computer database and printed for the reviewer to check against. Beginning in 1998, the Principal Investigators of the Clinical Centers are requested to listen to the tape of one case and one control each quarter following the same procedures outlined above.

A sample of the study forms from each Clinical Center are entered into the central database by Clinical Coordinating Center staff. Beginning January 1998 specific forms are requested on a regular schedule for this quality control program. The Clinical Center data file is compared to the CCC file, and the number of errors is tabulated by whether the error was made by Clinical Center staff or CCC staff. Systematic errors are bought to the attention of the staff making these errors. A summary of these comparisons is included in the Quarterly Performance Report.

14.2.3 Site Visits

In addition to preparing the Clinical Center performance monitoring reports, the CCC staff insure data quality by conducting periodic site visits or audit visits to the Clinical Centers. Tape recordings of two cases and two controls (selected in advance by CCC staff) are reviewed in the same way as described in Section 14.2.2. The data on the records for these cases and controls are compared against listings of data residing on the main database at the CCC as of the date of the request for a site visit. Using the data as of the site visit request should prevent any auditprompted revisions of the data form(s). Spirometry tracings, chest X-ray reports, and pathology reports for cases are reviewed by the site visit team. Consent forms and the Laboratory Forms (Form 10) are reviewed for both cases and controls. Plans for site visits and site visit requests are provided to the Study Chairperson and NHLBI Project Office on a schedule agreed to with the NHLBI Project Office. Site visit reports summarize the findings of the site visit and are sent to the Study Chairman, Clinical Center Principal Investigator, the NHLBI Project Officer and members of the Data and Safety Monitoring Board. Recertification of Clinical Center personnel responsible for key areas of data collection may also be necessary during site visits.

14.2.4 Quality Control for Chest X-rays

A chest X-ray for each case is obtained for ACCESS. These X-rays are read by Clinical Center ACCESS physicians. A sample of ACCESS X-rays is selected and submitted to a panel of ACCESS physicians for independent assessment during the Steering Committee meetings. The repeat classifications are compared to the original classifications. Discrepancies between the two readings are summarized using the kappa statistic.

14.2.5 Quality Control for Pathology Slides

A 10% random sample of pathology slides obtained in ACCESS is collected at the CCC and sent to other ACCESS pathologists for interpretation. The two interpretations are compared using the kappa statistic.

14.2.6 Monitoring Data Quality of Spirometry and Biological Specimen Analysis at the Clinical Centers and the Core Facilities

Two methods are used to monitor the reliability of test results from the Clinical Centers and the core facilities: 1) examination of means or frequencies of key variables (e.g., results of assays) over time using control charts; and 2) duplicate interpretation of study materials. Monitoring means and

frequencies of key variables with control charts allows CCC staff to determine if and when these distributions change. Since routine changes are unexpected, an investigation is undertaken to determine whether the shift represents a change in reporting by the Clinical Center or core facility or a change in the population being studied. Results from the duplicate sample submissions are compared to assess reliability: using Kappa statistics for categorical data, Spearman's rank order correlation coefficients for ordinal data, and Spearman or Pearson correlation coefficients for continuous data. In addition, the intra-class correlation coefficients are calculated for continuous or ordinal measures.

For spirometry measures, tracings for a random sample of procedures are sent to the Study Chairman to determine whether the tracings are acceptable. For biological specimen analysis, a random sample of biological specimens is requested by the CCC staff for duplicate evaluation. The duplicate is marked in such a way that the pathologist can not determine that this specimen is part of the quality control program. The results of the two duplicate tests are compared.

Results of some tests to be performed in ACCESS can vary widely under different testing conditions. For example, it has been suggested that polymerase chain reaction (PCR) technology can detect viral DNA or RNA at concentrations as low as one sequence per 10,000 cells (Busch et al, 1992). Such high levels of sensitivity require that the PCR tests are performed under exacting conditions with no possibility of contamination (Bitsch et al, 1992). The conditions for these sensitive assays are stated in Volume IV of the Procedures Manual.

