6.1 CASE DEFINITION

All cases should have a clinical course compatible with sarcoidosis, that is, a systemic granulomatosis of unknown etiology. All cases selected for inclusion in the study have tissue confirmation of granuloma. The Kveim test may be used to confirm a diagnosis of sarcoidosis in patients with Löfgren's Syndrome (defined by the presence of erythema nodosum), if no other tissue is obtained. Kveim agent may be used for tissue confirmation only in cases with Löfgren's Syndrome. Investigators using the Kveim agent must adhere to the U.S. Food and Drug Administration (FDA) Investigational New Drug (IND) Application requirements for use of this agent. Standardized procedures for interpretation of the Kveim biopsies are described in the IND documentation and the ACCESS Procedures Manual Volume I.

Intrathoracic disease documented by mediastinal lymph node or transbronchial biopsies does not require clinical evidence of other organ involvement. A patient with a positive biopsy of a skin lesion requires involvement of at least one other organ as defined in Table 6-1. Table 6-1A provides the categories in use starting November 1996. Revisions to this table were made in April 1998 (Table 6-1B), but did not change the diagnostic criteria. Cases with uveitis on slit lamp examination require a biopsy of other involved tissue.

Tissue samples are considered positive for sarcoidosis if they demonstrate non-caseating granuloma and are read as being compatible with a diagnosis of sarcoidosis, without other possible causes. All biopsies are reviewed by a single pathologist at each Clinical Center for quality control purposes. The Clinical Center Principal Investigator reports the pathologist's level of certainty of the diagnosis of the presence of granuloma as definite, possible, and clearly not. If the tissue is interpreted as a possible or probable diagnosis, the Clinical Coordinating Center identifies pathologists at other Clinical Centers who review the slides (including special stains) in question as an unknown sample as part of the quality control program.

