6.2 CASE SELECTION

It is planned that the total study population will consist of 720 cases and 720 controls. Each Clinical Center enrolls, interviews, examines and collects blood specimens from 72 cases with sarcoidosis and enrolls, interviews and collects blood specimens from 72 matched controls during the recruitment period (November 1, 1996 through June 30, 1999).

Cases may be recruited from a variety of clinical settings, including inpatient, hospital-based outpatient, and non hospital-based outpatient. Each Principal Investigator defines, in advance, the geographic area from which the center recruits patients for the study. Permission to contact patients identified in a clinical setting must be obtained initially from the attending physician of record, in advance of study enrollment. Potential cases are informed that a payment will be given to reimburse them for parking costs, meals and other expenses (including lost time from work) at the medical center, and transportation costs.

At the time of enrollment into the study, patients are categorized according to their clinical condition at the time of initial diagnosis, i.e., the day of biopsy confirmation. Table 6-2A outlines the disease categories that were used to describe cases beginning November 1996. An additional revised classification system was used beginning September 1997 and is given in Table 6-2B. The purpose of revising the disease categories is to encourage use of information on facets of the clinical presentation of sarcoidosis that were not readily appreciated in the hierarchical, initial classification of disease categories. This information is used in ACCESS to assess the spectrum of clinical sarcoidosis presentations represented among the ACCESS cases.

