8.4 CLOSE-OUT PROCEDURES

ACCESS controls and the ACCESS cases not enrolled in the Clinical Course Study are closed-out of the study once all information for the entry evaluation has been collected and edited. ACCESS cases enrolled in the Clinical Course Study are closed-out after the completion of the 24-month examination. As part of the close-out procedures, cases and controls are thanked for their participation in ACCESS. They are notified that at the end of ACCESS, a brief description of the study results will be sent to them if they inform Clinical Center staff of their interest.

TABLE 8-1

ACCESS STUDY FORMS AND DATA AND SPECIMEN COLLECTION

	CAS	CONTROLS		
Activity (Form)	Baseline Evaluation	24-Month Follow-up	Baseline Evaluation	
Questionnaires 15-19	R		R	
Relationship Questionnaire A (Form 20)	R		R	
Relationship Questionnaire B (Form 21)	CR1		CR1	
Family History Questionnaire (Form 22)	R		R	
Family History Supplement (Form 23)	CR2		CR2	
Physical Examination Form (Form 24)	R	R		
Laboratory Data Form (Form 25)	R	R		
Spirometry with Pre- & Post- Bronchodilators	R	R		
Complete Blood Count and Differential	R	R		
Biochemistry	R	R		
Baseline Questionnaire for Cases Only (Form 26)	R			
Follow-up Questionnaire for Cases Only (Form 27)		R		
Telephone Contact Summary (Form 28)		R*		
Chest Radiography Interpretation Form (Form 30)	R	R		
Chest X-Ray	R	R		
Diagnostic Specimen Report (Form 31)	R			
Tissue Biopsy	R			

R =	Required
-----	----------

- R* =
- R+ =
- Required at 6, 12 and 18 months after enrollment. Required if available from clinically indicated evaluations. Required if initial diagnosis of sarcoidosis is probable or possible. R++ =
- Required if participant has biological children. CR1 =
- Required if participant has more than nine siblings. CR2 =

TABLE 8-1 (Continued)

ACCESS STUDY FORMS AND DATA AND SPECIMEN COLLECTION

	CAS	CONTROLS	
Activity (Form)	Baseline Evaluation	24-Month Follow-up	Baseline Evaluation
Bronchoalveolar Lavage (BAL) Form (Form 32)	R+		
Tissue Sample Shipping form (Form 40)	R++		

- R Required =
- R* =
- Required at 6, 12 and 18 months after enrollment. Required if available from clinically indicated evaluations. R+ =
- Required if initial diagnosis of sarcoidosis is probable or possible. R++ =
- Required if participant has biological children. CR1 =
- Required if participant has more than nine siblings. CR2 =

FIGURE 8-1

- 1a) Entry evaluation (questionnaires)
- 1b) Telephone contact
- 1c) Follow-up questionnaire

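### Kappa alone on re-read pathology slides does not show whether cases are confirmed, because the slides come from people selected for a positive first reading

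*Protocol*

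**What the plan says.** Protocol section 14.2.5 describes the check: "A 10% random sample of pathology slides obtained in ACCESS is collected at the CCC and sent to other ACCESS pathologists for interpretation". It then gives the statistic: "The two interpretations are compared using the kappa statistic". It does not say which categories enter kappa, whether kappa is weighted, or what is reported beside it.

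Section 6.1 sets the entry condition: "All cases selected for inclusion in the study have tissue confirmation of granuloma". It defines a positive sample this way: "Tissue samples are considered positive for sarcoidosis if they demonstrate non-caseating granuloma and are read as being compatible with a diagnosis of sarcoidosis". The local reading is recorded in grades, as the "level of certainty of the diagnosis of the presence of granuloma as definite, possible, and clearly not". Doubtful tissue has its own route: "If the tissue is interpreted as a possible or probable diagnosis, the Clinical Coordinating Center identifies pathologists at other Clinical Centers who review the slides". Table 8-1 likewise has a shipping form for cases, marked "Required if initial diagnosis of sarcoidosis is probable or possible".

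On numbers, section 6.2 says: "It is planned that the total study population will consist of 720 cases and 720 controls". Section 7.2 limits controls to an interview, a questionnaire and a blood sample, so controls supply no slides.

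**The concern.** Kappa compares observed agreement with the agreement expected from the two readers' marginal distributions. It is informative when both readers use more than one category reasonably often. Here the material has been filtered on the first reader's answer: a slide enters the pool because someone read granuloma on it, and no provision is made for slides from non-cases. One margin is therefore constant or nearly so, and expected agreement comes close to observed agreement.

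The question this check should answer is how often a second pathologist, at another center, would not call an enrolled case a case. Every case-control odds ratio rests on that classification. A low kappa could prompt needless re-review when nearly all cases are confirmed. A moderate kappa could conceal several that are not.

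**Working it through.** The protocol gives no kappa value, target or sample size for this check, so there is no figure to reproduce.

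**Inputs**
- Cases: 720 (section 6.2). Sample: 10% (section 14.2.5). 0.10 × 720 = 72 slides, assuming one slide set per case.
- First reading: graded definite / possible / clearly not (section 6.1).
- Share of possible first readings: not stated. Values from 2 to 22 of 72 are assumed.

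**Formula** (unweighted): kappa = (po − pe)/(1 − pe), where po is observed agreement and pe is the agreement expected from the margins.

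**1. Reading scored positive/negative.** The first reader is positive on every slide and the second on a proportion q. Then po = q and pe = 1 × q + 0 × (1 − q) = q, so kappa = 0 for every q below 1 and 0/0 at q = 1.

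| Second reading positive | po | pe | kappa |
|---|---|---|---|
| 72/72 | 100% | 100% | undefined |
| 70/72 | 97.2% | 97.2% | 0 |
| 58/72 | 80.6% | 80.6% | 0 |
| 36/72 | 50.0% | 50.0% | 0 |

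**2. Graded reading, 4 of 72 first readings possible (68 definite).** Three different second readings give the same raw agreement, 68/72 = 94.4%:

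- *Four definite slides downgraded to possible, none refuted.* pe = (68 × 64 + 4 × 8)/72² = 4384/5184 = 0.8457. Kappa = (0.9444 − 0.8457)/(1 − 0.8457) = 0.64.
- *The same four called clearly not, so four cases refuted.* pe = (68 × 64 + 4 × 4)/5184 = 4368/5184 = 0.8426. Kappa = (0.9444 − 0.8426)/(1 − 0.8426) = 0.65.
- *All 72 called definite, so every case confirmed.* pe = (68 × 72)/5184 = 0.9444 = po. Kappa = 0.

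Kappa is marginally higher with four refuted cases than with none, and zero when every case is upheld.

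**3. Other assumed shares of possible.** The same three second readings give:

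| First readings possible | Four downgraded | Four refuted | All called definite |
|---|---|---|---|
| 2 | 0.48 | 0.49 | 0 |
| 4 | 0.64 | 0.65 | 0 |
| 7 | 0.75 | 0.75 | 0 |
| 14 | 0.84 | 0.84 | 0 |
| 22 | 0.88 | 0.88 | 0 |

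The level of kappa moves with the unknown share of possible. At no share does it separate a downgrade from a refutation.

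**4. Instability.** Suppose both readers call 70 slides definite and 2 possible, so pe = (70² + 2²)/5184 = 0.9460.
- Four disagreements: po = 94.4%, kappa −0.03.
- Two disagreements: po = 97.2%, kappa 0.49.
- No disagreements: po = 100%, kappa 1.00.

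**5. Proportion confirmed, exact (Clopper–Pearson) 95% interval**
- 72/72 = 100% (95.0% to 100%)
- 70/72 = 97.2% (90.3% to 99.7%)
- 58/72 = 80.6% (69.5% to 88.9%)

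The last two results, which positive/negative kappa cannot tell apart, have intervals that do not overlap.

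**The case against.** The strongest reply is that the protocol does not set up a two-category table. Section 6.1 grades the local reading and expects some readings below definite, and Table 8-1 provides a form for them. On that scale kappa is defined, rises with agreement and reaches 1 when the readers agree throughout. This stands. A reader might infer from the entry condition that kappa must be zero or undefined however well the pathologists agree. That requires a constant first reading, which the protocol does not impose. How skewed the margins are depends on a share that the document does not give.

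A second reply is that the sample is of slides obtained in the study, not expressly the one qualifying slide per case, so some negative slides could enter. That is possible. But nothing provides for slides from non-cases, so negatives would be incidental.

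A third is that the diagnosis has other safeguards. One pathologist per center reviews all biopsies, doubtful slides go to other centers as unknowns, and site visits review pathology reports. Section 14.2.6 adds masked duplicates of biological specimens. These count, and they rule out reading 14.2.5 as the only check on diagnosis. However, the cross-center review in 6.1 is triggered by doubtful readings, site visits look at reports, and 14.2.6 does not say that it covers diagnostic slides. The 14.2.5 sample is the only routine second reading by another pathologist stated for slides called definite.

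Finally, no threshold, eligibility rule or odds ratio depends on this kappa, and the cross-table behind it already holds the counts. This limits the harm and also makes the remedy nearly free.

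**Conclusion.** The point holds in a limited form. Scored positive/negative, kappa is 0 at 97% and at 80% confirmation alike and undefined at 100%; this is exact and needs only that the first reading is always positive. On the graded scale kappa is usable but answers another question. Under the assumed 4 of 72 possible first readings it is 0.64, 0.65 and 0 for none refuted, four refuted and all called definite. It therefore reflects the definite/possible boundary rather than case confirmation, and when nearly all first readings are definite a few slides move it widely.

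The sizes rest on one slide set per case, unweighted kappa, and an assumed share of possible readings and pattern of disagreement. The documents support neither a claim that kappa is always degenerate here nor a claim that the study's odds ratios are affected. The defect is that the one statistic named does not report what this quality check is for.

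**What to change.** In section 14.2.5, make the main measure the proportion of sampled cases whose granuloma is confirmed on the second reading, with an exact 95% interval. State which grades count as confirmed. Keep kappa as a supplement on the definite/possible/clearly-not scale, and print the full cross-table beside it so that downgrades and refutations can be told apart.

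The cost is a change of wording and one more line of reporting. No extra slides or readers are needed. Adding archived negative slides, so that both answers can occur, would be optional and is not required.
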